#### Sensitivity analysis

The overall response rate (including the breakdown for complete response and response) will be described at each scheduled visit of the intervention period.

The estimation of the response rate at D85 and its exact 95% confidence interval using Clopper-Pearson method will also be computed in participants who had an evaluable response at this visit.

Additional sensitivity analyses and subgroup analyses (eg, for primary wAIHA and SLE-associated wAIHA) may be performed and will be detailed in the SAP.

### **9.4.3 Secondary endpoint(s)**

#### **9.4.3.1 Part A (Cohorts 2 and 3 only)**

##### **9.4.3.1.1 Analysis of efficacy**

The following analysis of clinical response and fatigue will be conducted in the efficacy population of Part A for Cohorts 2 and 3 only. Response data will be listed for participants from all cohorts.

#### **Overall response rate at Day 85**

The overall response rate (including the breakdown for complete response and response) will be described by dose level group at each visit of the intervention period including Day 85 and using the same approach for participants with a non-evaluable response as in [Section 9.4.2.2](#).

#### **Time to response and durability of response**

The proportion of participants with durable hemoglobin response by Day 169 will be computed together with its exact 95% confidence interval.

The proportion of overall response will be computed at Day 169. Participants whose response at Day 169 is not evaluable, whatever the reason (eg, early discontinuation), will be considered as non-responders.

The overall response rate (including the breakdown for complete response and response) will be described by dose level group at each visit of the follow-up period.

The time to response (CR or R) will be computed as the time between the start of treatment until the first documented response (in days) and described by summary statistics (using n, mean, standard deviation, interquartile range, median, minimum, and maximum)

The time to loss of response (in days) will be computed as the time between the first documented response (CR or R) and the first documented loss of response (ie, neither R nor CR as detailed in [Section 3](#)) and described by summary statistics (using n, mean, standard deviation, interquartile range, median, minimum, and maximum). For participants still showing a response at the end of the follow-up period, the end date will be the last date where the response is assessed.

Depending on the number of responses, the time to response and the time to loss of response will be listed or described by dose level group in the subset of participants who achieved a response during the intervention period as well as in the subset of participants who achieved a response during the study including the follow-up period (if different).

The time to loss of CR (in days) will be computed as the time between the first documented CR and the first documented loss of CR (as detailed in [Section 3](#)) and described by summary statistics (using n, mean, standard deviation, interquartile range, median, minimum, and maximum). For participants still showing a CR at the end of the follow-up period, the end date will be the last date where the response is assessed.

Depending on the number of CRs, the time to loss of CR will be listed or described by dose level group in the subset of participants who achieved a CR during the intervention period as well as in the subset of participants who achieved a CR during the study including the follow-up period (if different).

The proportion of participants requiring rescue therapy (any wAIHA-directed therapy other than prednisone or transfusion) or splenectomy will also be described by dose level group.

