Part A (Cohorts 2 and 3 only)	

• To evaluate the efficacy of isatuximab in adults with wAIHA.

• Overall response rate (response (R) or complete response (CR)) at Day 85.

R is defined as an increase in hemoglobin by <math>\geq 2</math> g/dL from baseline and an absence of transfusion in the last 7 days and absence of rescue medications in the past 4 weeks. Biochemical evidence of hemolysis may still be present.

CR is defined as hemoglobin <math>\geq 11</math> g/dL (women) or <math>\geq 12</math> g/dL (men), no evidence of hemolysis (normal bilirubin, LDH, haptoglobin, and reticulocytes), and absence of transfusion in the last 7 days and absence of rescue medication in the past 4 weeks.

• Proportion of participants with durable hemoglobin response by Day 169. Durable response is defined as Hb level <math>\geq 10</math> g/dL with an increase from baseline of <math>\geq 2</math> g/dL on three consecutive evaluable visits during the study period; with absence of transfusion and no rescue medication during the period of 3 consecutive visits and for at least 7 days (transfusions) and 4 weeks (rescue medication) prior to the first consecutive visit.

• Overall response rate at Day 169, median time to R or CR, median time to loss of R or CR (loss of R defined as hemoglobin <math>< 10</math> g/dL at two consecutive visits at least 7 days apart and initiation of new treatment for anemia or increase in steroid dose; loss of CR is defined as hemoglobin <math>< 11</math> g/dL (women) or <math>< 12</math> g/dL (men) at two consecutive visits at least 7 days apart), proportion of participants requiring rescue therapy (any wAIHA-directed therapy other than prednisone or transfusion) or splenectomy.

Objectives	Endpoints

 
To evaluate the impact of isatuximab treatment on fatigue.
 
 
Part B
 
 
To evaluate the safety and tolerability of isatuximab in adults with wAIHA.
 
To evaluate the durability of response to isatuximab and time to response.
 
	
 
FACIT-fatigue scale score at Day 85 and Day 169.
 

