1.2 MODIFICATIONS FROM THE STATISTICAL SECTION OF THE PROTOCOL

This study stopped early and, as a result, Part B was not performed. Therefore, all protocol defined analyses planned for Part B will not be presented.

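### Time to loss of response pools ongoing responders with observed losses, so a finite median time to loss can be reported when nobody has lost response

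*Protocol*

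**What the plan says.** Protocol Table 2 names "median time to loss of R or CR" among the secondary endpoints for Part A Cohorts 2 and 3.

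Section 9.4.3.1.1 (Time to response and durability of response) defines time to loss of response as the days from first documented R or CR to "the first documented loss of response (ie, neither R nor CR as detailed in" Section 3). It attaches ordinary summary statistics: n, mean, SD, interquartile range, median, minimum and maximum. Participants "still showing a response at the end of the follow-up period, the end date will be the last date where the response is assessed". The rule is repeated for complete response: "For participants still showing a CR at the end of the follow-up period, the end date will be the last date" on which response was assessed.

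Whether a summary appears at all depends on the number of responses: "the time to response and the time to loss of response will be listed or described by dose level group". No threshold is given.

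The SAP leaves the end-date rule alone. Section 1.2 removes Part B: "Therefore, all protocol defined analyses planned for Part B will not be presented". Section 1.2.1 replaces the interquartile range with the SEM, keeps the mean and median, and separately changes which laboratory's results are used. Section 1.3 lists two six-dose labels, 280 mg and 560 mg, so the rule remains live for Cohorts 2 and 3.

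**The concern.** An ongoing responder's time to loss is unknown beyond the last assessment. The plan enters the follow-up time as if it were the time to loss, in the same mean and median as real losses. Each such value is capped at 169 minus the day of first response. Lasting responses are understated, and a later onset automatically gives a shorter apparent time to loss. Because Table 2 names a median, a median is the statistic a reader will expect.

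A bare listing of durations has the same ambiguity. A value of 112 days is a loss for someone first responding on Day 29 and losing response on Day 141 (141 − 29). It is an ongoing response for someone first responding on Day 57 and still responding on Day 169 (169 − 57).

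Two related gaps affect the same variable:

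- The end-date rule covers those still responding at the end of follow-up. It does not clearly cover a responder who leaves early without a documented loss.
- Section 9.4.3.1.1 describes loss as being in neither R nor CR. For loss of R, Table 2 requires hemoglobin below 10 g/dL at "two consecutive visits at least 7 days apart and initiation of new treatment for anemia or increase in steroid dose". These are different events.

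**Working it through.** The plan gives no figure for this endpoint. Its only sample-size calculation, Table 6, reproduces (N=14: 0.230 to 0.770, half-width 0.270) but does not bear on the point.

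**Inputs.** Visit days (15, 29, 43, 57, 71, 85, 113, 141, 169) come from the Schedule of Activities, with a ±7-day window at Day 169. Section 4.1 plans 3 participants per cohort. The documents give no response data, so the response and loss days below are hypothetical.

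**Cap on an ongoing value.** Duration = 169 − day of first response: 154 days for Day 15, 140 for Day 29, 112 for Day 57, 84 for Day 85, each within the visit window.

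**1. No losses.** First responses on Days 29, 57 and 85 give 140, 112 and 84 days.
- Plan: median 112; mean 336/3 = 112; SD = √[(28² + 0² + 28²)/2] = 28; SEM = 28/√3 ≈ 16.
- Losses: 0 of 3. Kaplan-Meier median: not reached.
- Two responders (Days 29 and 85) or one (Day 57) also give a median of 112 with no losses.

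**2. One loss.** The Day 29 responder loses response at Day 113 (84 days); the other two are ongoing at 112 and 84 days.
- Plan: median 84; mean 280/3 ≈ 93.
- Kaplan-Meier: survival falls to 1 − 1/3 = 0.67 at 84 days and no further, so the median is not reached.

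**3. Comparing two doses.**

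| | First response | Outcome | Durations | Plan median | Kaplan-Meier median |
|---|---|---|---|---|---|
| Dose A | Days 15, 29, 43 | all lost at Day 141 | 126, 112, 98 | 112 | 112 |
| Dose B | Days 57, 71, 85 | none lost | 112, 98, 84 | 98 | not reached |

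The plan's medians favour the dose where everyone lost response.

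**4. How often a group would have no losses.** Assume exponential loss with true median M, and first response equally likely on Days 29, 43, 57, 71 and 85. The chance that one responder is counted as ongoing at Day 169 is p = the average over onset days d of 2^(−C/M). The lower figure uses C = 169 − d (loss seen exactly). The higher uses C = 141 − d (loss dated at the next scheduled visit and confirmed at the one after, so Day 141 is the latest datable loss). For k responders the chance of no losses is p^k.

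| True median (days) | k = 1 | k = 2 | k = 3 |
|---|---|---|---|
| 60 | 28–39% | 8–15% | 2–6% |
| 120 | 53–62% | 28–38% | 15–24% |
| 180 | 65–73% | 42–53% | 28–38% |
| 365 | 81–85% | 65–73% | 53–62% |

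As a check where losses come early, 400,000 simulated groups for each k at M = 60 gave a typical plan median of 60–62 days with exact loss dates and 70 days with visit-based dates. There is no downward bias in that case.

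**5. The two descriptions of loss.** Take a participant with persisting hemolysis and baseline hemoglobin 9.5 g/dL. At 11.6 the rise is 2.1 and R is met (given no recent transfusion or rescue). At 11.0 the rise is 1.5, so R fails; hemolysis rules out CR. The participant is in neither R nor CR, but has not met the Table 2 loss, because hemoglobin is not below 10. If this persists to Day 169 and the Table 2 definition governs, the participant is neither still responding nor lost, and no end date is defined.

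**The case against.** The best case against is about consequence. The measure is secondary and descriptive, the protocol plans no formal test, cohorts have 3 planned participants, and Part B was not run. With so few responders, listing is the natural choice. Section 9.4.3.1.1 also states "Response data will be listed for participants from all cohorts" and requires response rates by dose at each follow-up visit. In example 3, if dose A's losses persisted, the Day 169 rates of 0/3 and 3/3 would stand beside the medians. That example is also constructed for contrast, and time to loss does not drive dose decisions. All of this stands as a limit on the harm. It does not make a pooled median correct, and neither document commits to listing.

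Other points carry some weight:

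- The end of follow-up could be read as each participant's own end, which would cover early leavers. That is a fair reading, so this part is a wording gap.
- The cross-reference to Section 3 could be meant to import the Table 2 loss definition. The text supports both readings, which is why it needs settling.
- The percentages in step 4 rest on assumptions without a source in the documents. They omit onset at Day 15, and the higher figure is not an upper bound, since Table 2 also requires a treatment change for loss of R. They indicate scale only.
- The SAP defers to a sponsor reporting guideline that is not available here, so the final display cannot be fully judged. Nothing in the two documents says it adds censoring or a flag.
- A Kaplan-Meier median on one to three responders adds little. True; the count of losses and the flagged listing matter more.

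**Conclusion.** The concern holds. Followed as written, the rule gives a finite median time to loss with no losses: 112 days in example 1, where censoring gives not reached. This follows from the rule itself; the assumed response days only set the number. It applies to loss of response and loss of CR in Cohorts 2 and 3 whenever the times are summarised.

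Under the assumptions of step 4, a group with three responders would have no losses 28–38% of the time at a true median of 180 days, and 2–6% at 60 days. Where losses are early and nearly all observed, the bias is small or absent.

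The Part A safety endpoint, the Day 85 and Day 169 response rates and the durable-response proportion do not use this rule. It should be fixed, but it does not threaten the main results.

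**What to change.** State in the SAP:

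1. By dose level, report the number of losses over the number of responders, and list each duration with a lost/ongoing flag. At this sample size that carries most of the information.
2. Censor responders without a documented loss, including those who leave early, at their last response assessment.
3. If a median is given, use the Kaplan-Meier median and allow it to be not reached. Drop the mean, SD and SEM for time to loss of response and time to loss of CR.
4. Reconcile the loss event in Section 9.4.3.1.1 with the definition in Section 3, so that one definition governs.

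The cost is SAP wording and one flag per responder, with no new data. Some medians will be reported as not reached, at least as often as groups have no losses.

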### **Fatigue**

Descriptive statistics of the FACIT-fatigue scale score will be provided for the value at each scheduled visit of the intervention and follow-up periods (including Day 85 and Day 169) and on the change from baseline by dose level group.

#### **9.4.3.2 Part B**

##### **9.4.3.2.1 Analysis of safety**

All the safety analyses will be performed using the safety population. Statistical analysis of safety data will be conducted following the same approach as described in [Section 9.4.2.1](#).

##### **9.4.3.2.2 Secondary efficacy endpoints**

Analysis of secondary efficacy endpoints will be conducted in the efficacy population. Subgroup analyses (eg, for primary wAIHA and SLE-associated wAIHA) may be performed and will be detailed in the SAP.

### **Time to response and durability of response**

The proportion of overall response at Day 169 and its exact 95% confidence interval using Clopper-Pearson method, the time to response and durability of response, and the proportion of participants requiring rescue therapy or splenectomy will be summarized, using the same approach and definitions as in [Section 9.4.3.1.1](#).

### **Fatigue**

Descriptive statistics of the FACIT-fatigue scale score will be provided for the value at each scheduled visit of the intervention and follow-up periods (including Day 85 and Day 169) and on the change from baseline.

In addition, a mixed-effect model for repeated measures will be implemented providing estimates and 95% confidence intervals at Day 85 and Day 169 for the change from baseline: the full model specifications will be provided in the SAP.

### **9.4.3.3 Parts A and B**

#### **9.4.3.3.1 Other secondary efficacy endpoints**

##### **Markers of hemolysis**

To evaluate the effect of isatuximab on markers of hemolysis, the values and change from baseline at each scheduled visit in LDH, haptoglobin, reticulocytes, and total bilirubin will be described.

##### **Hemoglobin**

Descriptive statistics and graphs of hemoglobin values and change from baseline over time for each scheduled visit will be provided.

#### **9.4.3.3.2 Analysis of pharmacokinetic parameters**

Descriptive statistics (eg, mean, geometric mean, median, SD, SEM, CV, minimum, and maximum) for the pharmacokinetic parameters of isatuximab will be provided by dose level, under the responsibility of the Sanofi Pharmacokinetics, Dynamics and Metabolism (PKDM) department.

#### **9.4.3.3.3 Immunogenicity**

Anti-Drug Antibodies (ADA) incidence will be described. Individual ADA sample status (positive, negative or inconclusive) will be listed.

### **9.4.4 Tertiary/exploratory endpoint(s)**

The analysis described below will be performed for Parts A and B.

#### **9.4.4.1 Pharmacodynamic analysis**

PD biomarkers (eg, levels of circulating immune cells, immunoglobulin levels, vaccine antibody titers, bone marrow plasma cells) will be described or plotted in the Pharmacodynamic population. Additional details will be provided in the SAP.

#### **9.4.4.2 Pharmacokinetic/pharmacodynamic analysis**

The analysis of PK/PD relationship (eg, relationship of PK parameters to hemoglobin levels and levels of plasmablasts and NK cells) will be described and reported separately.

### **9.4.5 Other safety analyse(s)**

Any other safety analyses will be detailed in the SAP.

#### **9.4.6 Other analyse(s)**

Not applicable.

### **9.5 INTERIM ANALYSES**

No formal interim analysis is planned. For Part A, a descriptive summary may be provided on key parameters of interest after each cohort for decision making on the dose.

The study analysis will be conducted in two steps. The first step analysis will be conducted when all participants in Part B have completed Day 85 (and including 30 days after the last IMP administration) or withdrawn from the intervention period. The final analysis will be conducted at the end of the study.

### **9.6 COMMITTEES OR OTHER REVIEW BOARDS**

For details on Dose Selection Committee refer to Appendix 1 ([Section 10.1.5](#)).

## 10 SUPPORTING DOCUMENTATION AND OPERATIONAL CONSIDERATIONS

### 10.1 APPENDIX 1: REGULATORY, ETHICAL, AND STUDY OVERSIGHT CONSIDERATIONS

#### 10.1.1 Regulatory and ethical considerations

- This study will be conducted in accordance with the protocol and with the following:
  - Consensus ethical principles derived from international guidelines including the Declaration of Helsinki and the applicable amendments and Council for International Organizations of Medical Sciences (CIOMS) International Ethical Guidelines.
  - Applicable ICH Good Clinical Practice (GCP) Guidelines.
  - Applicable laws and regulations (eg, data protection law as General Data Protection Regulation - GDPR).
- The protocol, protocol amendments, ICF, Investigator Brochure, and other relevant documents (eg, advertisements) must be submitted to an IRB/IEC by the Investigator and reviewed and approved by the IRB/IEC before the study is initiated.
- Any amendments to the protocol will require IRB/IEC approval before implementation of changes made to the study design, except for changes necessary to eliminate an immediate hazard to study participants.
- The Investigator will be responsible for the following:
  - Providing written summaries of the status of the study to the IRB/IEC annually or more frequently in accordance with the requirements, policies, and procedures established by the IRB/IEC. Determining whether an incidental finding should be returned to a participant and, if it meets the appropriate criteria, to ensure the finding is returned (an incidental finding is a previously undiagnosed medical condition that is discovered unintentionally and is unrelated to the aims of the study for which the tests are being performed). The following should be considered when determining the return of an incidental finding:
    - The return of such information to the study participant (and/or his/her designated healthcare professional, if so designated by the participant) is consistent with all applicable national, state, or regional laws and regulations in the country where the study is being conducted, and
    - The finding reveals a substantial risk of a serious health condition or has reproductive importance, AND has analytical validity, AND has clinical validity.
    - The participant in a clinical study has the right to opt out of being notified by the Investigator of such incidental findings. In the event that the participant has opted out of being notified and the finding has consequences for other individuals, eg, the finding relates to a communicable disease, Investigators should seek independent ethical advice before determining next steps.

- In case the participant has decided to opt out, the Investigator must record in the site medical files that she/he does not want to know about such findings.
- Notifying the IRB/IEC of SAEs or other significant safety findings as required by IRB/IEC procedures.
- Providing oversight of the conduct of the study at the site and adherence to requirements of 21 CFR, ICH guidelines, the IRB/IEC, European regulation 536/2014 for clinical studies (if applicable), and all other applicable local regulations.

As applicable, according to Directive 2001/20/EC, the Sponsor will be responsible for obtaining approval from the Competent Authorities of the EU Member States and/or Ethics Committees, as appropriate, for any amendments to the clinical trial that are deemed as “substantial” (ie, changes which are likely to have a significant impact on the safety or physical or mental integrity of the clinical trial participants or on the scientific value of the trial) prior to their implementation.

#### **10.1.2 Financial disclosure**

Investigators and sub-Investigators will provide the Sponsor with sufficient, accurate financial information as requested to allow the Sponsor to submit complete and accurate financial certification or disclosure statements to the appropriate regulatory authorities. Investigators are responsible for providing information on financial interests during the course of the study and for 1 year after completion of the study.

#### **10.1.3 Informed consent process**

- The Investigator or his/her representative will explain the nature of the study to the participant or his/her legally authorized representative and answer all questions regarding the study.
- Participants must be informed that their participation is voluntary. Participants or their legally authorized representative will be required to sign a statement of informed consent that meets the requirements of 21 CFR 50, local regulations, ICH guidelines, Health Insurance Portability and Accountability Act (HIPAA) requirements, where applicable, and the IRB/IEC or study center.
- The medical record must include a statement that written informed consent was obtained before the participant was enrolled in the study and the date the written consent was obtained. The authorized person obtaining the informed consent must also sign the ICF.
- Participants must be re-consented to the most current version of the ICF(s) during their participation in the study.
- A copy of the ICF(s) must be provided to the participant or the participant's legally authorized representative.

Participants who are rescreened are required to sign a new ICF.

The ICF will contain a separate section that addresses the use of remaining mandatory samples or new extra samples for optional exploratory research. The Investigator or authorized designee will

explain to each participant the objectives of the exploratory research. Participants will be told that they are free to refuse to participate and may withdraw their consent at any time and for any reason during the storage period. A separate consent will be required to document a participant's agreement to allow any remaining specimens to be used for exploratory research. Participants who decline to participate in this optional research will not provide this separate consent.

For a regional or national emergency declared by a governmental agency, contingency procedures may be implemented for the duration of the emergency (See [Section 8](#)).

The participant or their legally authorized representative may be verbally informed prior to initiating any changes that are to be implemented for the duration of the emergency (eg, study visit delays/treatment extension, use of local labs).

